A single case of reversible Grade 3 renal insufficiency was observed at the 250 mg TID dose level, characterized by a Grade 3 elevation in creatinine that recurred upon rechallenge at a lower dose. Thirteen other events of elevated creatinine (all Grade 1-2) have been noted in patients receiving monotherapy CB-839 across the three ongoing studies (10%) at doses up to 1000 mg TID.

Two events of Grade 3 mucositis/stomatitis have been observed at the 600 mg BID dose

level, both in patients with AML. Three other Grade 1/2 stomatitis events have occurred with CB-839, two of which were AML patients receiving monotherapy and one event was in an RCC patient receiving CB-839 in combination with everolimus, for which stomatitis is a well-known adverse event. Given the absence of events in patients receiving monotherapy CB-839 in non-AML patients, it is not clear if mucositis is clearly CB-839 related at this time or if it is just associated with the underlying disease (AML) or concomitant medication (everolimus).

Overall, the safety and tolerability profile of CB-839 supports the continued development of CB-839 in patients with advanced solid and hematological malignancies.

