### **4.1. Inclusion Criteria**

Patients must meet all of the following inclusion criteria to be eligible for enrollment into the study:

1. Signed and dated written informed consent.
2. Male or female  $\geq 18$  years of age.
3. Histologically or cytologically-confirmed diagnosis of metastatic *KRAS* wildtype colorectal cancer (CRC).
4. Eastern Cooperative Oncology Group (ECOG) performance status of 0 or 1.
5. In Dose Escalation, patients must have had at least one prior line of chemotherapy for advanced disease or progressed within 6 months of adjuvant therapy (prior chemotherapy and/or anti-EGFR therapy is permitted).

6. In Dose Expansion, patients must have received prior anti-EGFR therapy and achieved at least stable disease on at least one scan as their best response.
7. In Dose Expansion, patients must be willing to undergo a pre-treatment biopsy, and two research PET imaging techniques (F-FSPG), one at pre-treatment and one after one cycle of treatment.
8. In Dose Expansion, at least one measurable lesion as defined by RECIST 1.1 which can be followed by CT or MRI.
9. Adequate organ function including:
  - Absolute neutrophil count (ANC)  $\geq 1,500/\mu\text{L}$
  - Platelets  $\geq 100,000/\mu\text{L}$
  - Serum albumin  $\geq 3.0 \text{ g/dL}$
  - Serum creatinine  $\leq 2 \text{ mg/dL}$ , or calculated creatinine clearance  $> 50 \text{ mL/min}$  (per the Cockcroft-Gault formula)
  - Total bilirubin  $\leq 1.5$  times upper limit of normal (ULN)
  - Aspartate transaminase (AST) and Alanine Aminotransferase (ALT)  $\leq 5.0 \times \text{ULN}$ .
10. Women of childbearing potential (WOCBP) must have a negative serum pregnancy test within 14 days prior to receiving first dose of protocol-indicated treatment; and additionally agree to use at least 2 methods of acceptable contraception (Appendix 4) or abstain from heterosexual intercourse from the time of signing consent, and until 2 months after patient's last dose of protocol-indicated treatment.

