## **10.2. Dose-Adjustments and Delays of CB-839**

Given the limited number of patients treated to date and the open label, nonrandomized nature of the studies to date, the safety profile of CB-839 has not been fully established. An overall summary of the available safety and tolerability data was profiled above in section 2.4.2.

Overall, CB-839 has been well tolerated across all dose levels tested to date. The large majority of toxicities that have been observed to date have been Grades 1 and 2 and manageable with supportive care and/or interruption of study drug.

Careful application of the dose-escalating rules and close observation of the subjects should minimize the potential risk of dosing with CB-839.

Based on available data, adverse events that are most likely to be observed with CB-839 treatment are mild to moderate and include fatigue, gastrointestinal events (nausea, vomiting, anorexia), photophobia and elevated liver function tests.

Photophobia and related ocular toxicities (e.g., photopsia) have been identified as CB-839-related events. In almost all cases, these events have been Grade 1 and generally do not have an impact on the patient's daily life, although one Grade 2 event required the patient rest for 1-2 hr in a dark room. These events appear to occur around Cmax (1-4 hr after dosing) and resolve with time. Anecdotal reports suggest that tachyphylaxis develops and these events tend to become less frequent over extended dosing. More severe cases can be managed with dose reduction and the use of sunglasses may be considered.

The study personnel must be able to recognize and diagnose these potential adverse events and initiate prompt intervention. In particular, regular monitoring of liver function tests and renal function is recommended.

**Upon withholding CB-839 for adverse event, CB-839 may be restarted when the associated adverse event has returned to  $\leq$  Grade 1, or to the patient's baseline value. (The baseline value is defined as the most immediately known value in place prior to patient's first receipt of CB-839 on Cycle 1, Day 1.)**

**For adverse events deemed by the investigator to be clinically significant and as possibly, probably, or definitely related to CB-839 treatment:**

- **Grade 1 or 2:** Manage with appropriate supportive care.
- **Grade 3 or 4:** Hold CB-839 and Dose Reduce (by 1 or more dose levels) upon resumption

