### **Reporting period**

Adverse events experienced by participants will be collected and reported from initiation of protocol-indicated treatment for Phase I patients. For Phase II patients, AEs will be collected and reported from the time of the first research scan. AEs will be tracked for all patients in both phases throughout the study through 28 days after the last dose of protocol-indicated treatment. Participants who experience an adverse event related to a study procedure and/or protocol-indicated treatment beyond 28 days will continue to be contacted by a member of the study team until the event is resolved, stabilized, or determined to be irreversible by the participating investigator.

Laboratory and vital sign abnormalities are to be recorded as Adverse Events only if they are medically relevant as judged by the investigator (e.g. symptomatic, requiring corrective treatment, leading to discontinuation and/or fulfilling a seriousness criterion). Unless otherwise specified by protocol or a patient's study physician, abnormal laboratory values of Grade 1 and Grade 2 will be deemed Not Clinically Significant (NCS) and are not required to be individually noted or recorded within the study data.

Baseline disease-related signs and symptoms which are initially recorded as medical history, will subsequently be recorded as adverse events during the trial if they worsen in severity or increase in frequency.

Participants should be instructed to report any serious post-study event(s) that might reasonably be related to participation in this study. The investigator should notify the IRB and any other applicable regulatory agency of any unanticipated death or adverse event occurring after a participant has discontinued or terminated study participation that may reasonably be related to the study.

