Otherwise we will continue accrual up to 29. If 4 or more patients experience BOR among 29 treated, we reject the null hypothesis ( $p < 0.05$ ) of low efficacy (BOR  $\leq 5\%$ ) and declare this regimen sufficiently active in this patient population to warrant further study in more definitive trials. Assuming low efficacy, the probability of early termination is 60% with an expected sample size of 18.

Demographic information such as age, race, and sex, will be tabulated. Descriptive statistics, including means, standard deviations, and ranges for continuous parameters, as well as percentages and frequencies for categorical parameters, will be presented. Adverse medical events will be tabulated. NCI toxicity Grade 3 and Grade 4 laboratory abnormalities will be listed. All patients who received at least one cycle of the combination therapy will be included in the safety analyses.

Power Analysis:

Phase II: We assume a type I error of 5%. If the true RR with this triple agent therapy is 20% or greater, then 29 patients provide 80% power or more to declare this regimen sufficiently active to warrant further study.

Relationship between change in tumor size and radiotracer uptake: We will also evaluate the relationship between radiotracer uptake at baseline and change in tumor size at the time of objective response assessment using a standard linear regression analysis. The slope will describe the shape of the relationship between  $SUV_{max}$  and change in tumor size, while the coefficient of determination ( $R^2$ ) describes the strength of the relationship between the two measures. A similar linear regression analysis will be conducted to quantify the relationship between the change in  $SUV_{max}$  as measured from baseline to after one cycle of therapy and change in tumor size.

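### Grade 1-2 laboratory values need not be captured and no baseline comparison is specified, so the frequency of mild creatinine, liver and magnesium changes may not be estimable

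*Combined protocol and SAP*

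**What the plan says.** **Recording.** Section 12.1 (Reporting period) sets a default for mild laboratory abnormalities: "abnormal laboratory values of Grade 1 and Grade 2 will be deemed Not Clinically Significant (NCS"). They "are not required to be individually noted or recorded within the study data". The sentence opens with an exception: "Unless otherwise specified by protocol or a patient's study physician". Just before it comes the route by which a laboratory value becomes an adverse event: "Laboratory and vital sign abnormalities are to be recorded as Adverse Events only if they are medically relevant as judged by the investigator". Section 12.5.1 is similar: a value counts as an adverse event only if it brings signs or symptoms, or needs treatment or further tests.

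**Analysis.** Section 15 says "NCI toxicity Grade 3 and Grade 4 laboratory abnormalities will be listed", and separately that adverse events will be tabulated. It names no other laboratory output: no shift table, no change from baseline, no summary by dose level.

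**Why these analytes are drawn.** Section 2.4.2 reports one Grade 3 renal event on CB-839, then: "Thirteen other events of elevated creatinine (all Grade 1-2) have been noted in patients receiving monotherapy CB-839". It also describes treatment-related liver test elevations as generally asymptomatic. Section 10.2 adds that "regular monitoring of liver function tests and renal function is recommended". The study calendar (Section 6.1, note 6) puts creatinine, ALT, AST, total bilirubin and magnesium in the chemistry panel drawn on Days 1 and 15 of every cycle.

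**The concern.** The trial measures these five analytes about every two weeks, but the default rule does not require mild abnormal values to reach the study data, and the planned output starts at Grade 3. Almost all the creatinine events in the protocol's own background lie below that threshold.

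Baseline matters too. Section 4.1 admits patients with AST and ALT up to 5 x ULN. Section 10.1 sets transaminase DLT limits according to whether the patient was Grade 1 or Grade 2 at entry, so the protocol itself accepts that a raw on-study grade depends partly on the starting value. A listing of raw grades without the entry value cannot separate a large rise from normal from a small rise on a high baseline. It would also leave out a patient who moved from normal to Grade 2.

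What is at stake is the descriptive safety profile. Safety and tolerability is the Phase I primary objective (Section 3.1). Section 2.5 names further definition of the safety profile among the secondary aims, and Section 2.4.2 says that the profile of CB-839 is not fully established.

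**Working it through.** **Inputs**
- 147 monotherapy patients, 1 Grade 3 renal event and 13 Grade 1-2 creatinine events, stated as 10% (Section 2.4.2).
- Up to 12 patients in Phase I; 10 in Phase II stage 1 and 29 in all (Section 15). Full accrual is 12 + 29 = 41. A stop after stage 1 gives 12 + 10 = 22.

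**Reproducing the stated rate.** 14/147 = 9.5%, which rounds to the stated 10%. Using the thirteen alone, 13/147 = 8.8%. The background figure is consistent with its inputs.

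**Share below the listing threshold.** 13/14 = 92.9% were Grade 1-2 and 1/14 = 7.1% was Grade 3. None is reported as Grade 4.

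**Illustration for this trial.** Assume that the monotherapy rates carry over, with at most one event per patient. Expected events = n x 14/147. Expected Grade 3 events = n x 1/147. Chance that the Grade 3-4 listing shows no creatinine event = (146/147)^n.

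| n | Expected creatinine events | Expected Grade 3 | Chance that listing shows none |
|---|---|---|---|
| 41 | 41 x 14/147 = 3.9 | 41/147 = 0.28 | (146/147)^41 = 76% |
| 22 | 22 x 14/147 = 2.1 | 22/147 = 0.15 | (146/147)^22 = 86% |

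**Can a mild event reach the output by another route?**
1. *Protocol exception.* No section specifies otherwise for creatinine, ALT, AST, bilirubin or magnesium.
2. *Physician exception.* This allows capture patient by patient. Capture that varies between patients does not give a rate.
3. *Adverse event route.* This works for values judged medically relevant or acted on. An asymptomatic value that nobody acts on does not qualify under Section 12.1 or 12.5.1.
4. *Dose modification.* In Phase I, some Grade 2 laboratory toxicities may surface through the irinotecan dose-modification table (Section 10.4.1, Table 7), if attributed to irinotecan.

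What remains uncovered is the asymptomatic Grade 1-2 change that prompts no action.

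**The case against.** The strongest reply is that the rule is permissive and sits in the adverse event section. It says that values are not required, not that they are barred. It can be read as sparing sites from annotating each mild abnormality. The case report form content is not given, so the documents do not establish that scheduled chemistry values are left out of the database. This stands, and it limits the point to what need not be captured.

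Four stronger readings are tempting, and the documents do not support them:
- A reader might infer that renal toxicity would go unreported or that the plan is blind to it. Medically relevant abnormalities of any grade would be tabulated as adverse events, Grade 3-4 values would be listed, and SAE and DLT reporting is untouched.
- A reader might infer that the listing excludes baseline. Section 15 is silent on baseline, and a patient-level listing could show it.
- A reader might infer that the 14 events are an established drug effect. Section 2.4.2 notes the thirteen milder ones without attributing them to CB-839, and creatinine is not among the common reactions in Section 12.2.
- A reader might infer that CB-839 has never before been given with panitumumab. The documents do not say so.

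The size is also open to challenge. The background pools doses up to 1000 mg TID, while this trial doses twice daily with food, for which Section 2.4.2 describes a better safety profile. The figure of 41 needs full accrual and mixes a triplet with a doublet. Section 15 itself gives a 60% chance of stopping after stage 1 under low efficacy. This is why 22 is shown beside 41 and both are labelled as illustration.

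Finally, full capture would still give imprecise rates: 4 of 41 has an exact 95% interval of 2.7% to 23.1%, and 1 of 12 has 0.2% to 38.5%. That rules out a formal comparison with the monotherapy rate. It does not remove the value of describing the changes.

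**Conclusion.** The point holds as a cheap improvement to safety reporting, not as a flaw in a primary decision. By default, asymptomatic Grade 1-2 changes in creatinine, ALT, AST, bilirubin or magnesium that prompt no action need not enter the study data. No baseline-to-worst summary is specified, so their frequency may not be estimable.

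The share that rests directly on the documents is 13 of 14 creatinine events at Grade 1-2. The projections (3.9 events in 41 patients or 2.1 in 22) rest on monotherapy rates carrying over from other doses and schedules, and on one event per patient. The MTD decision runs on DLTs and the Phase II decision on response rate, so neither depends on this.

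**What to change.** In Section 12.1, state that all scheduled values of creatinine, ALT, AST, total bilirubin and magnesium are entered in the study data whatever their grade, with no need to log each one as an adverse event.

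In Section 15, keep the Grade 3-4 listing and add a table of baseline grade by worst on-study grade for these analytes. Give with it the maximum ratio to baseline, or the minimum value for magnesium. Present it by phase and dose level in the safety population as Section 15 defines it, descriptively and without testing.

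The cost is modest extra data entry or electronic transfer of values already drawn, plus one table. No new tests, visits or staff are needed, and no dose or clinical rule changes.

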### **12.2. Risks Associated with CB-839**

- The more common adverse reactions (seen in  $\geq 10\%$  of patients) of CB-839 include: fatigue, abnormal liver function tests (alanine aminotransferase, aspartate transaminase, and alkaline phosphatase), and nausea.
- The less common adverse reactions (5-10%) of CB-839 include: anemia, vomiting, discomfort in the eyes due to light exposure and sensitivity to light, and decreased appetite.
- A more detailed safety profile of CB-839 is provided in the investigator's brochure.

### **12.3. Risks Associated with Panitumumab and Irinotecan**

- The most common adverse reactions ( $\geq 20\%$ ) of panitumumab as monotherapy are: skin rash with variable presentations, paronychia, fatigue, nausea, and diarrhea.
- The most common adverse reactions ( $\geq 20\%$ ) in clinical trials of panitumumab in combination with FOLFOX chemotherapy are: diarrhea, stomatitis, mucosal inflammation, asthenia, paronychia, anorexia, hypomagnesemia, hypokalemia, rash, acneiform dermatitis, pruritus, and dry skin.
- Common adverse reactions ( $\geq 30\%$ ) observed in single agent therapy clinical studies of irinotecan are: nausea, vomiting, abdominal pain, diarrhea, constipation, anorexia, neutropenia, leukopenia (including lymphocytopenia), anemia, asthenia, fever, body weight decreasing, alopecia.
- Common adverse reactions ( $\geq 30\%$ ) observed in combination therapy clinical studies of irinotecan are: nausea, vomiting, abdominal pain, diarrhea, constipation, anorexia, mucositis, neutropenia, leukopenia (including lymphocytopenia), anemia, thrombocytopenia, asthenia, pain, fever, infection, abnormal bilirubin, alopecia.
- A more detailed safety profile of panitumumab and irinotecan are provided in the respective product labels, currently locatable online via following:

**Panitumumab (VECTIBIX):**

[http://pi.amgen.com/united\\_states/vectibix/vectibix\\_pi.pdf](http://pi.amgen.com/united_states/vectibix/vectibix_pi.pdf)

**Irinotecan (CAMPTOSAR):**

[http://labeling\(pfizer.com>ShowLabeling.aspx?format=PDF&id=533](http://labeling(pfizer.com>ShowLabeling.aspx?format=PDF&id=533)

### **12.4. Risks Associated with $^{18}\text{F}$ -FSPG PET/CT (optional for Phase I and required for Phase II) and $^{11}\text{C}$ -Glutamine PET/CT (optional for Phase I only)**

- Both the PET and CT expose the subject to radiation.
- Patients should not be pregnant while on this study because the imaging agent being tested contains a small amount of radioactivity. This could affect an unborn baby.
- Risks and side effects related to the IV catheter may include discomforting pain at the site of injection, bleeding, and bruising.

## 12.5. Safety Parameters and Definitions

### 12.5.1 Adverse Event (AE)

An adverse event is any undesirable sign, symptom or medical condition or experience that develops or worsens in severity after starting the first dose of study treatment or any procedure specified in the protocol, even if the event is not considered to be related to the study.

Abnormal laboratory values or diagnostic test results constitute adverse events only if they induce clinical signs or symptoms or require treatment or further diagnostic tests.

### 12.5.2 Serious adverse event (SAE)

A serious adverse event is an undesirable sign, symptom or medical condition which:

- is fatal or life-threatening;
- requires or prolongs inpatient hospitalization;
- results in persistent or significant disability/incapacity;
- constitutes a congenital anomaly or birth defect; or
- jeopardizes the participant and requires medical or surgical intervention to prevent one of the outcomes listed above.

Events **not** considered to be serious adverse events are hospitalizations for:

- routine treatment or monitoring of the studied indication, not associated with any deterioration in condition, or for elective procedures
- elective or pre-planned treatment for a pre-existing condition that did not worsen
- emergency outpatient treatment for an event not fulfilling the serious criteria outlined above and not resulting in inpatient admission
- respite care

## 12.6. Assessment of Adverse Events

All AEs and SAEs, whether volunteered by the patient, discovered by study personnel during questioning, or detected through physical examination, laboratory test, or other means, will be reported appropriately. Each reported AE or SAE will be described by its duration (i.e. start and end dates), regulatory seriousness criteria if applicable, suspected relationship to the investigational treatment (see following guidance), and actions taken.

To ensure consistency of AE and SAE causality assessments, investigators should apply the following general guidelines:

- **Yes**

There is a reasonable causal relationship between the investigational treatment and the adverse event. There is a plausible temporal relationship between the onset of the AE and administration of the investigational treatment, and the AE cannot be readily explained by the patient's clinical state, intercurrent illness, or concomitant therapies; and/or the AE follows a known pattern of response to the investigational treatment; and/or the AE abates or resolves upon discontinuation of the investigational treatment or dose reduction and, if applicable, reappears upon re-challenge.

- **No**

There is no reasonable causal relationship between the investigational treatment administered and the adverse event. Evidence exists that the AE has an etiology other than the investigational treatment (e.g. pre-existing medical condition, underlying disease, intercurrent illness, or concomitant medication); and/or the AE has no plausible temporal relationship to administration of the investigational treatment.

#### **12.6.1 Expectedness**

- **Expected:** Expected adverse events are those that have been previously identified as resulting from administration of the agent. For the purposes of this study, an adverse event is considered expected when it appears in the current adverse event list, the Investigator's Brochure, the package insert or is included in the informed consent document as a potential risk.
- **Unexpected:** An adverse event is considered unexpected when it varies in nature, intensity or frequency from information provided in the current adverse event list, the Investigator's Brochure, the package insert or when it is not included in the informed consent document as a potential risk

